STUDY PROTOCOL PLAN AND STADISTICAL ANALYSIS PLAN (SAP)

UNIVERSITY CEU CARDENAL HERRERA

Principal investigator: [name] [name]

TITLE: Textural Analysis and Effect of ROI Size on Infrared Thermography in Athletes With Patellar Tendinopathy. A Cross-sectional Study

Research and Ethics Committee of University Católica San Antonio, Number: CE111803

NCT ID:

DATE: 07-23-2025

STUDY PROTOCOL PLAN

Objectives:

The objectives of our study have been the following:

The objectives of this study were: (1) to evaluate differences in thermal and GLCM-based textural features between athletes with PT and healthy controls; (2) to compare the diagnostic performance of IT and GLCM features applied to thermographic images; and (3) to identify the most appropriate ROI size for optimal characterization of PT using both thermal and textural analysis.

Volunteers who want to participate in the study will read the general information of the study and sign the informed consent to participate in the study.

Once the informed consent has been read and delivered, the evaluator will check that they meet the inclusion criteria.

Participants will be divided into two groups: (1) athletes with unilateral PT, diagnosed using a combination of clinical criteria, specific functional tests, and ultrasound evaluation. Additional inclusion criteria for this group included a symptom duration of more than 3 months, a VISA-P score of less than 80, and a differential diagnosis to rule out other possible causes of anterior knee pain; (2) healthy volunteer athletes, recruited under the inclusion criteria of no previous history of PT and a VISA-P score of 100.

Participants with any other lower limb pathology, nerve or vascular disorder, or skin lesion in the knee area that could alter the thermal information of the patellar tendon region will be excluded from both groups.

All participants were instructed not to engage in physical exercise; not to drink alcohol, coffee or energy drinks 12 hours before the measurements; not to smoke in the previous 6 hours; not to apply creams or lotions to their legs to avoid altering skin emissivity; to report any medication or treatments they were taking; and to try to avoid altering their rest and meal habits. These requirements minimise the influence of individual extrinsic factors on the IT results.

Recorded variables

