Demographic and clinical characteristics (gender, age, BMI, and duration of evolution) will be recorded. The severity of patellar tendinopathy will be measured using the widely accepted and valid Victorian Institute of Sport Assessment-Patella (VISA-P) questionnaire. All thermal image recordings were performed by the same researcher.

Determination of sample size

The sample size will be calculated using G*Power v.3.1.9.7 software (Heinrich-Heine University) for a logistic regression design to evaluate the diagnostic accuracy of IT in distinguishing between patients with PT and healthy controls, taking into account the possible inclusion of covariates. The parameters are set as follows: odds ratio = 5, alpha error probability $\alpha = 0.05$, power $1-\beta = 0.80$, R^2 for other covariates = 0.1, binomial distribution with a proportion $\pi = 0.5$.

Image acquisition protocol

TI images will be recorded with an OPTRIS PI 450 IRT camera coupled to Optris PI Connect software (Germany). The IRT camera has a noise equivalent temperature difference <40 mK with a field of view of $38^\circ \times 29^\circ$, a wide temperature range of -20 °C to $+100$ °C, a spectral range of $7.5-13$ μ m, a focal plane array sensor size of 382×288 pixels, an emissivity set to 0.98, and a measurement uncertainty of $\pm 2\%$ of the global temperature reading. The capture frame size was 55.4×40.63 cm (1.5 mm/px).

The participant will acclimatise in an isolated room (3.86×3.47 m²), without temperature sources, at an average temperature of (23.7 ± 0.9 °C) and relative humidity of ($49 \pm 5\%$) for 15 minutes without clothing on the lower extremities. The participant will sit on a hydraulic stretcher with their feet on a step to isolate contact with the floor, and the camera will be positioned perpendicular to the subjects for a more accurate reading. Two rectangular ROIs will be selected on each knee using a previously described method by superimposing ROIs on thermal images using markers on the skin. a) an ROI of the patellar tendon (tendon ROI); b) an ROI of the anterior part of the knee (knee ROI) using the anatomical references of the upper pole of the patella, anterior tibial tuberosity, and lateral contour of the knee.

Statistical Analysis Plan (SAP)

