The data will be analysed using IBM SPSS Statistics for Windows v.25.0 (IBM Company, 2017). The normality and homoscedasticity of the variables will be checked. The data will be summarised using absolute and relative frequencies for categorical variables, and means \pm standard deviations (SD) and 95% confidence intervals for continuous variables.

Independent sample t-tests will be used to compare continuous variables, and a chi-square test will be used to compare categorical variables at baseline between PT patients and controls.

One-way analysis of covariance will be used to analyse the thermal difference and textural characteristics between PT patients and healthy controls, controlling for the effects of clinical and demographic covariates. Cohen's d statistic will be calculated to assess the effect size (d > 0.1 small, around 0.3 medium, and >0.5 large).

To calculate the diagnostic accuracy of the thermal difference and textural characteristics based on first- and second-order statistical analysis, simple logistic regression will be performed for age, sex, and BMI by group, including them in subsequent models if $p < 0.20$. Sensitivity (Se), specificity (Sp) and Youden's index (expressed as $Se + Sp - 1$) will be investigated, as well as the positive and negative likelihood ratios (LRp and LRn) of thermal difference, textural characteristics and their combinations. The thermal difference and textural characteristics will be introduced one by one and in all possible combinations (255 models) in the logistic regression analyses, including a maximum combination model containing all characteristics.

Receiver operating characteristic (ROC) curves will be used and the Hosmer-Lemeshow goodness-of-fit test will be performed by comparing the observed and expected frequencies of the outcome variable ($p > 0.05$ indicates a good fit). The Brier score will be calculated to evaluate the accuracy of the probabilistic predictions, where lower scores indicate better model performance. An area under the curve (AUC) value close to 90% and sensitivity and specificity values above 80% are considered acceptable.

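### Does leaving the covariates of the PT-versus-control ANCOVA unnamed put the Objective 1 comparison at risk?

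*Combined protocol and SAP*

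**What the plan says.** The ANCOVA paragraph of the Statistical Analysis Plan (SAP) compares the thermal and texture measures between PT athletes and controls, "controlling for the effects of clinical and demographic covariates". It gives no list. It then grades effect sizes as "d > 0.1 small, around 0.3 medium, and >0.5 large".

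Two other places bear on what the covariates might be:

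- Under Recorded variables: "Demographic and clinical characteristics (gender, age, BMI, and duration of evolution) will be recorded". VISA-P is recorded as the severity measure in the next sentence.
- In the SAP's logistic regression paragraph: "simple logistic regression will be performed for age, sex, and BMI by group", with those that pass a p < 0.20 screen carried into later models.

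The group definitions in the Study Protocol Plan require, for PT athletes, "a symptom duration of more than 3 months, a VISA-P score of less than 80". Controls must have "no previous history of PT and a VISA-P score of 100".

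**The concern.** The phrase in the ANCOVA sentence resembles the label on the list of recorded characteristics, and that list contains duration of evolution. A reader who took the list as the covariate set would be adjusting a between-group comparison for something that only one group can have. VISA-P has the same difficulty: it is below 80 in one group and fixed at 100 in the other, so the two groups do not overlap.

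The awkward case is duration coded 0 in controls. The model then runs without complaint, but its group coefficient compares controls with PT athletes extrapolated to zero duration, a state their eligibility rules out. That is not the Objective 1 contrast, and its standard error is inflated. An open covariate set could also, in principle, be chosen after the results are seen.

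**Working it through.** **Which variables does the plan tie to adjustment?**

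| Variable | Exists in both groups? | Named for a model? |
|---|---|---|
| Age, sex, BMI | Yes | Yes, in the logistic paragraph |
| Duration of evolution | No (PT only, inferred from eligibility) | No |
| VISA-P | Yes, but without overlap (<80 v 100) | No |

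The list under Recorded variables says what is collected. The ANCOVA sentence does not refer to it, and the noun and word order differ. With age, sex and BMI the ANCOVA is sound.

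**What if duration were entered anyway?** The documents give no duration distribution and no sample size, so r, CV and the group sizes below are assumptions.

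1. *Duration blank in controls.* The complete cases contain no controls and the design matrix has rank 2 of 3. The group effect cannot be estimated, and the analyst sees this at once.

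2. *Duration coded 0 in controls, size of the shift.* The duration slope comes from PT alone, so the group coefficient equals the raw difference minus slope × mean duration. The slope is r × SD(feature)/SD(duration). In PT SD units the shift is therefore −r/CV.
   - |r| = 0.1: 0.1/0.5 = 0.20 down to 0.1/2 = 0.05.
   - |r| = 0.3: 0.3/0.5 = 0.60 down to 0.3/2 = 0.15.
   - r = 0: no shift.

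   The direction follows the sign of r. A simulation with 400,000 per group agreed with the formula to within 0.004.

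3. *Duration coded 0 in controls, precision.* With equal groups, the R² of group on duration is 1/(1 + 2CV²), and the SE is multiplied by 1/√(1 − R²) = √(1 + 1/(2CV²)).
   - CV 0.5: √3 = 1.73.
   - CV 1: √1.5 = 1.22.
   - CV 2: √1.125 = 1.06.

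4. *Illustration.* Assume 30 per group, a true difference of 0.80 SD, mean duration 15 months and a slope of 0.02 SD per month. The expected shift is 0.02 × 15 = 0.30, and simulation gave 0.50 instead of 0.80. Across assumed CVs of 0.5 and 1, and slopes of 0 and 0.02, power was about 85–87% without duration and 19–68% with it.

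**What if the set were picked after seeing results?** Null data were simulated with 20 to 50 per group (6,000 data sets per cell), taking the smallest p over every covariate subset.
   - 8 subsets of age, sex and BMI: 6.3–7.1% false positives per feature, against a nominal 5%.
   - 16 subsets once zero-coded duration is allowed: 8.6–12.6%.

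These are upper bounds, because they assume deliberate selection of the best result.

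**Would the slip go unnoticed?** The SAP plans a baseline comparison of continuous variables between groups, and checks of normality and equal variance. A zero-coded duration would appear there as a control mean of 0 with no variance, and VISA-P as 100 with no variance. Neither looks like a usable covariate.

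**The case for a change.** The strongest case for changing the text is that the gap is real and cheap to close. No sentence carries age, sex and BMI back to the ANCOVA. Those three hardly account for the word clinical, except perhaps BMI. The one item in the recorded list that is plainly clinical is duration. The zero-coded model fails silently, and one added sentence would rule it out.

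Some of this stands: the covariates are not named, and the formulas above are correct. It falls short for three reasons.

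- The harmful reading is not in the document. It needs a sequence of choices that no section supports, and a trained analyst would not adjust a case-control contrast for disease duration.
- The suggestion that images may already exist before the covariates are settled rests on one past-tense sentence, "All thermal image recordings were performed by the same researcher". The Image acquisition protocol section describes the same images in the future tense, and tenses are mixed throughout.
- The obvious wordings are no clear improvement. Pointing to the logistic models would import the p < 0.20 screen and make the set depend on the data. Using what participants are asked to disclose ("to report any medication or treatments they were taking") as a further covariate could bring in treatment given for PT itself, and so a milder form of the same problem.

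**Conclusion.** No change to the plan is called for. The ANCOVA sentence leaves out a detail that analysts would fill sensibly, most naturally with the age, sex and BMI that the SAP names one paragraph later. On that reading the Objective 1 contrast is sound and nothing is lost.

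The shift of 0.05 to 0.60 SD and the SE multipliers of 1.06 to 1.73 apply only if duration is entered and coded 0 in controls, which the document nowhere says. They also rest on assumed values of r and CV. Without that step, the most that free choice among age, sex and BMI could do is raise the per-feature error rate from 5% to about 6–7%, and only under deliberate selection at the assumed 20 to 50 per group. That controls have no duration is itself an inference from eligibility, though a firm one. Naming the covariates would record the set probably intended; it would not give a better analysis.

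### Age, sex and BMI enter the diagnostic models because they separate the groups, but no covariate-only reference is planned, so under imbalance part of the absolute accuracy reported for thermography may be demographic

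*Combined protocol and SAP*

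**What the plan says.** All of this is in the Statistical Analysis Plan section unless stated.

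- **Purpose of the step:** "To calculate the diagnostic accuracy of the thermal difference and textural characteristics based on first- and second-order statistical analysis".
- **Covariate rule:** "simple logistic regression will be performed for age, sex, and BMI by group, including them in subsequent models if" p < 0.20. A covariate is kept according to how strongly it is associated with being a PT athlete or a control.
- **Models:** "The thermal difference and textural characteristics will be introduced one by one and in all possible combinations (255 models) in the logistic regression analyses".
- **Attribution:** sensitivity, specificity and Youden's index are to be examined, "as well as the positive and negative likelihood ratios (LRp and LRn) of thermal difference, textural characteristics and their combinations". No covariate is named here.
- **Benchmark:** "An area under the curve (AUC) value close to 90% and sensitivity and specificity values above 80% are considered acceptable".
- **Sample size section:** the logistic design is meant "to evaluate the diagnostic accuracy of IT in distinguishing between patients with PT and healthy controls, taking into account the possible inclusion of covariates".
- **Recruitment (study protocol plan):** controls are "healthy volunteer athletes, recruited under the inclusion criteria of no previous history of PT and a VISA-P score of 100". No matching on age, sex or BMI is described.

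The plan also has baseline t-tests and a chi-square test, and an ANCOVA that adjusts group means for clinical and demographic covariates. It does not say which model each accuracy figure comes from.

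**The concern.** Adjusting for covariates is sound when estimating an association. Diagnostic accuracy is different: the AUC of a model with a feature and covariates describes the whole prediction, not the feature. Here the covariates are chosen because they predict group. If the figures come from those models and are reported as the accuracy of thermography, any demographic separation between the two recruited groups is credited to the camera.

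That share belongs to the recruitment, so it would not carry over to an athlete population with a different mix. The absolute figures are at stake, because they are what the benchmark is applied to and what a reader would take away. The ANCOVA does not help, since it adjusts feature means and not AUC, sensitivity, specificity or likelihood ratios. Hosmer-Lemeshow and the Brier score assess the whole model, covariates included.

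**Working it through.** **1. Is a covariate-only model among those planned?** The number of non-empty subsets of k features is 2^k − 1. With k = 8, 2^8 − 1 = 255, which matches the SAP. The 8 is inferred, not stated. The empty feature set, which would be the covariate-only model, would make 256, so it is not included. The one-covariate screening fits come earlier and serve as a p-value filter; no AUC is planned for them.

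**2. How often does the rule act?** With no true imbalance and three independent covariates, at least one enters with probability 1 − 0.8³ = 48.8%.

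**3. Study size.** No total is stated, so there is none to reproduce. The stated inputs (OR 5, alpha 0.05, power 0.80, R² 0.1, proportion 0.5) need a baseline probability p1 and a sidedness that are not given. By the Hsieh formula, two-sided, with p1 assumed 0.4:

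- odds = (0.4/0.6) × 5 = 3.33, so p2 = 0.769 and the mean probability is 0.585
- n = [1.96·√(0.585·0.415/0.5) + 0.842·√(0.24 + 0.178)]² / [(0.369)²·0.5] ≈ 53.5
- 53.5/(1 − 0.1) ≈ 59.4, rounded up to 60

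For p1 from 0.1 to 0.5, one- or two-sided, the Hsieh and Wald formulas give 45 to 105 in total. The illustration uses 30 per group.

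**4. Simulation.** Each covariate is screened at p < 0.20, the logistic model is fitted with one feature plus the retained covariates, and the apparent (in-sample) AUC is taken. The feature is independent of the covariates. Assumed imbalances:

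- mild: 80% vs 70% male, age and BMI d = 0.2
- larger: 85% vs 65% male, age d = 0.5, BMI d = 0.4

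| Mean AUC, 2000 replicates | None | Mild | Larger |
|---|---|---|---|
| Useless feature, alone | 0.558 | 0.559 | 0.558 |
| Retained covariates only (0.5 if none) | 0.563 | 0.613 | 0.722 |
| Useless feature + retained covariates | 0.604 | 0.643 | 0.736 |
| d = 1.2 feature, alone | 0.801 | 0.801 | 0.801 |
| d = 1.2 feature + retained covariates | 0.812 | 0.824 | 0.859 |
| Same d = 1.2 models, new athletes, same mix | 0.790 | 0.794 | 0.823 |
| Same d = 1.2 models, balanced mix | 0.790 | 0.779 | 0.746 |

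Under larger imbalance the useless feature adds 0.736 − 0.722 = 0.014 to what the covariates already give. For the d = 1.2 feature the apparent lift is 0.859 − 0.801 = 0.058. In new athletes of the same mix the model reaches 0.823, against 0.802 for the feature alone, so about 0.02 is real demographic signal and the rest is optimism. In a balanced mix the same model falls to 0.746, below the feature alone. Under mild imbalance the apparent lift is 0.824 − 0.801 = 0.023, and none of it survives in new athletes (0.794).

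**5. Chance of meeting the whole benchmark** (AUC ≥ 0.88 taken as close to 90%, sensitivity and specificity both over 80% at one threshold; d = 1.2, 6000 replicates):

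| | None | Mild | Larger |
|---|---|---|---|
| Feature alone | 3.7% | 3.8% | 4.2% |
| With retained covariates | 5.7% | 8.3% | 22.1% |

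Under larger imbalance, an AUC cut of 0.85 gives 24.9% (5.6% alone) and a cut of 0.90 gives 16.9% (2.4% alone). At 50 per group the with-covariates figures are 2.6%, 3.0% and 16.6%, against 1–2% alone. A useless feature meets the benchmark in at most 0.3% of studies.

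**6. Other assumptions.** With 70 in total, age and BMI d = 0.5 and 75% vs 55% of one sex, a useless feature plus covariates gives 0.741 and the covariates alone 0.731. With imbalance in one variable only (sex 85% vs 65%, or age d = 0.5), a d = 1.2 feature gives 0.831 or 0.834 in the study and 0.803 or 0.805 in new athletes, so that lift is again mostly optimism.

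**7. Does the remedy work?** The likelihood-ratio test over the covariate-only model rejects for a useless feature in 5.5%, 4.7% and 5.0% of studies, and for d = 1.2 in 99.4%, 99.2% and 98.2%.

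**The case against.** **The report would show the imbalance.** This stands. The baseline tests and the screening regressions would reveal it; under larger imbalance, about 90% of simulated studies meeting the benchmark had a covariate at p < 0.05 in the screen. A reader might infer that the inflation would be invisible, and the plan does not support that. What is missing is the size of the demographic share.

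**A covariate-only fit already exists when one covariate is retained.** True: the screening regression is then that model. But no AUC is planned for it, and no joint fit is planned when two or three are retained.

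**For a useful feature the effect is mostly overfitting unless several covariates are imbalanced.** This stands, as steps 4 and 6 show. The 22% figure needs all three variables to be imbalanced in ways that add up, and the documents give no baseline data to suggest this.

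**The objectives are comparative.** Objective 2 is "to compare the diagnostic performance of IT and GLCM features applied to thermographic images", and objective 3 compares ROI sizes. The screen involves only the covariates and group, so the same covariates enter every model. Ranking is therefore much less affected. A reader might infer that these comparisons are invalid; that does not follow. The benchmark, however, is absolute.

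**Feature-only figures can be confounded too.** This stands. If the feature shares R² = 0.1 with the covariates (the sample size input), assumed to run in the direction of the larger imbalance, the feature-alone AUC for d = 1.2 rises from 0.80 to 0.85. Feature-only figures are therefore not a sufficient remedy.

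**The accuracy figures may be meant to come from feature-only models.** Possible, since the source model is not stated. But the screening sentence opens with diagnostic accuracy as its purpose, the sample size section allows for covariates in that same evaluation, and the 255 models are the only logistic models specified after the screen.

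**Conclusion.** The point holds in conditional form and should be corrected. On the natural reading of the SAP, and if the groups differ in age, sex or BMI, the absolute AUC, sensitivity, specificity and likelihood ratios reported for thermography include a demographic part that the planned analyses cannot separate.

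Its size depends on imbalance that is assumed, not shown. At 30 per group a useless feature moves from 0.56 to about 0.64 or 0.74, mostly from the covariates. A d = 1.2 feature moves from 0.80 to about 0.82, mainly through optimism, or to 0.86 under three-variable imbalance. If no covariate passes p < 0.20, the problem does not arise.

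A reader might also infer that the rule would let a worthless feature pass as diagnostic. The simulations do not support that: it met the whole benchmark in at most 0.3% of studies. The realistic risk is a moderately good feature carried towards or over the benchmark. Optimism from searching 255 models is a separate matter and was not simulated.

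**What to change.** 1. Fit a model with the retained covariates alone and report its AUC, sensitivity, specificity and Brier score. For every feature model that contains covariates, report the AUC increment over it with a confidence interval, and the likelihood-ratio test.
2. Beside these, report feature-only AUC, sensitivity, specificity and likelihood ratios as unadjusted figures, noting that they may be confounded if features vary with age, sex or BMI. When any covariate is retained, add a covariate-adjusted ROC.
3. Do not apply the 90%/80% benchmark to a covariate-containing model as the accuracy of thermography unless the covariate-only and feature-only figures stand beside it. Label the source model of each figure, and say so if no covariate was retained.

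Forcing all three covariates into every model is not a substitute: for a useless feature it raises the apparent AUC further (0.637, 0.670 and 0.747 for no, mild and larger imbalance).

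The cost is SAP wording and a few extra fits on variables already recorded. Headline accuracy may be lower.

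### The Objective 2 comparison is undefined, and setting a multi-feature texture model against the single thermal feature on apparent AUC would favour texture even at equal true accuracy

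*Combined protocol and SAP*

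**What the plan says.** The second objective (Study Protocol Plan, Objectives) is "to compare the diagnostic performance of IT and GLCM features applied to thermographic images".

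The analysis that serves it is in the diagnostic-accuracy paragraph of the Statistical Analysis Plan. It deals with "the thermal difference and textural characteristics based on first- and second-order statistical analysis". These "will be introduced one by one and in all possible combinations (255 models) in the logistic regression analyses", up to a model that holds all of them. For the models the SAP reports sensitivity, specificity, Youden's index, likelihood ratios, ROC curves, the Hosmer-Lemeshow test and the Brier score. It also sets a bar: "An area under the curve (AUC) value close to 90% and sensitivity and specificity values above 80% are considered acceptable".

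The SAP does not list the eight features that 255 models imply. It does not say which texture model is to be set against thermography, how a model would be chosen, or how two AUCs would be compared. It mentions no cross-validation, bootstrap, hold-out sample or optimism correction. It also does not say whether the 255 models are fitted once or separately for the tendon and knee ROIs.

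**The concern.** An AUC computed on the data that fitted the model is optimistic, and the optimism grows with the number of fitted terms. The thermal-only model has one feature term. A texture-only model may have up to seven. Read side by side without correction, the two AUCs are not on the same footing, and the difference leans towards texture.

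The plan leaves this comparison open. It produces many texture models of different sizes, states a performance bar that invites a look for models that clear it, and fixes no comparator. One of the three stated objectives could then end in the conclusion that texture outperforms thermography when the two are equally accurate, or when thermography is better.

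**Working it through.** **1. Model count.** Eight features give 2^8 − 1 = 255 non-empty subsets, which reproduces the SAP's figure. The thermal difference is always in the singular, so one thermal and seven textural features is the likely split: 1 thermal-only model, 2^7 − 1 = 127 texture-only models and 255 − 1 − 127 = 127 mixed models. This split is inferred. Objective 2 names GLCM features, which are second-order, while the SAP's wording also covers first-order statistics. With one first-order texture feature the GLCM-only count is 2^6 − 1 = 63; with two it is 2^5 − 1 = 31.

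**2. Sample size.** No N is stated, so there is none to reproduce. The stated inputs are an odds ratio of 5, alpha 0.05, power 0.80, R² 0.1 and a binary predictor with proportion 0.5. Sidedness and the baseline probability are not given.
- Two-sided with a 50:50 outcome: the proportions are 0.691 and 0.309, the two-proportion formula gives 51.4 in total, and 51.4/0.9 = 57.1, taken as 58 (29 + 29).
- Two-sided Wald formula with baseline probability 0.1: the second probability is 0.5/1.4 = 0.357. N = 7.849 × 2 × (1/0.090 + 1/0.2296)/(ln 5)² = 93.7, and 93.7/0.9 = 104.1, taken as 105.

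Over baseline probabilities from 0.1 to 0.5 the range is about 47–83 one-sided and 58–105 two-sided. The simulations cover N = 40 to 120.

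**3. Simulation at equal true accuracy.** Equal groups, Gaussian features and no covariates. The best possible texture rule has the same true AUC as the thermal feature. Texture features have correlation 0 or 0.5. All 127 texture-only logistic models are fitted and the highest apparent AUC is compared with the thermal one. At N = 40 to 120 and true AUC 0.70 or 0.80, texture came out ahead in 63–86% of studies, with a mean gain in AUC of +0.015 to +0.11. The Brier score favoured texture in 61–86%.

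**4. Search or number of terms?** Share of simulated studies in which texture has the higher apparent AUC (500 per row, texture correlation 0.5, thermal feature independent of texture unless stated; mean gain in brackets):

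| N | True AUC, both | Best of 127 | Full 7-feature model, no search |
|---|---|---|---|
| 64 | 0.50 | 98% (+0.135) | 97% (+0.128) |
| 64 | 0.70 | 81% (+0.071) | 79% (+0.066) |
| 64 | 0.80 | 72% (+0.042) | 70% (+0.039) |
| 64 | 0.90 | 73% (+0.030) | 71% (+0.028) |
| 64, thermal–texture correlation 0.7 | 0.80 | 83% (+0.044) | 80% (+0.041) |
| 46 | 0.80 | 77% (+0.064) | 75% (+0.059) |
| 106 | 0.80 | 63% (+0.024) | 63% (+0.021) |

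The two columns differ by about 1–3 percentage points and by less than 0.01 in AUC. The number of fitted terms therefore accounts for nearly all of the tilt. Repeats at 29 + 29, with one informative and six noise texture features, agree: the best texture model won in 95–99%, 77–84% and 72–77% at true AUC 0.50, 0.70 and 0.80, and the full model in 96–99%, 78–79% and 70–71%. When thermography was truly better (0.80 against 0.70), the best texture model still won in 36–41%, against 12–18% for one pre-named feature.

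**5. Fewer GLCM features.** At 29 + 29 and true AUC 0.50, 0.70 and 0.80, 63 candidate models gave wins of 95%, 76% and 66%; 31 gave 94%, 70% and 69%.

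**6. Like-for-like comparison.** One pre-named texture feature that truly equals thermography won in 41–56%. The best of the seven single-feature models won in 29–66%. At 29 + 29 it was near even at true AUC 0.70 and 0.80 (49% and 48%), but it won in 87% when nothing was informative.

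**7. Effect of validation.**
- Each model cross-validated by itself (29 + 29, 100 simulations): the full model won in 28% (true AUC 0.70) and 34% (0.80), but the best of the 127 cross-validated models won in 64% and 63%. The standard error is about √(0.64 × 0.36/100) = 5 points.
- Whole search repeated inside 5-fold cross-validation (N = 64): texture won in 30% (0.70) and 33% (0.80), with mean differences of −0.065 and −0.045.

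The second result partly reflects a real loss. At N = 60 and true AUC 0.80, a searched texture model reached about 0.76 on new data.

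**The case against.** The strongest reply is that the documents never say that the best texture model will be set against the thermal one. A reader might infer that Objective 2 is one model against 127. The text does not support this: it names no comparator, no selection rule and no best model. Its statement that "The thermal difference and textural characteristics will be introduced one by one" makes a feature-by-feature comparison at least as natural, and that shows little or no tilt for a pre-named feature. This stands, and it is why the point is conditional. It does not remove the gap, because the like-for-like comparison is not fixed either.

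A reader might also infer that the sheer number of texture models causes the bias, apart from ordinary overfitting. The calculations do not support that for apparent AUC, since the full model with no search does almost as well as the best of 127. Selection has a clear effect of its own only if models are validated singly and the best is then picked, which the SAP does not propose.

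The counts of 127, 63 and 31 are inferences, and the magnitudes depend on an N, true AUCs and feature distributions that the plan does not give. The models may also carry covariates ("simple logistic regression will be performed for age, sex, and BMI by group, including them in subsequent models if" p is below 0.20), which the simulations left out. These limits affect the size of the tilt. Its direction was the same in every equal-accuracy setting tried in which a multi-feature texture model was judged on apparent AUC.

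**Conclusion.** The concern holds in conditional form. Objective 2 has no defined comparison, and the analysis provided for it yields unvalidated accuracies for models of unequal size. If a multi-feature texture model is judged against the thermal difference on apparent AUC, texture would look better in roughly 63–86% of studies at an equal true AUC of 0.70 or 0.80, and in about 98% at N = 64 if neither method is informative. The main cause is up to seven fitted terms against one.

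The figures assume N between 40 and 120, Gaussian features, equal groups, no covariates and mostly a thermal feature independent of texture. Simulation error is about 2–3.5 percentage points, and somewhat more in the smallest runs. The documents do not show that a biased comparison is intended, only that nothing in the plan prevents it. This is an inexpensive improvement that should be made before analysis.

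**What to change.** In the SAP, before analysis:
- List the eight features, mark each as thermal, first-order or GLCM, and state whether the search is run per ROI.
- Define the Objective 2 comparison as the thermal difference against one pre-specified texture score of equal complexity, for example one named GLCM feature, with the same covariates in both models. Report the paired difference in AUC with its confidence interval.
- Label all other texture-only and mixed models exploratory.
- If a multi-feature or best texture model is quoted, report its performance only with the entire search and fitting repeated inside each bootstrap or cross-validation sample. Validating models one at a time and then picking the best is not enough.

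The cost is a short SAP revision and a few lines of code. There are three downsides. The headline texture AUC will be lower. The pre-named feature may not be the most discriminating one: where the texture signal was spread over all seven features, a single feature beat thermography in only 21% of simulations at N = 80 and true AUC 0.80, so a loss for that feature is not a loss for texture as a whole. Fully nested cross-validation also penalises a searched texture model at this sample size (it wins about 30–33% at N = 64 when true accuracy is equal), and the report should say so when it interprets the result.
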